6.9.2. Prohibited During the Study

Participants are required to discontinue and avoid using certain medications and treatments. Participants should be instructed at each visit to contact the study site investigator promptly if there are any intended changes or additions to concomitant medications. Prohibited medications during the study include:

- Oral and parenteral corticosteroids within 4 weeks prior to the first dose of study intervention.
- Current or anticipated use of protein therapeutics including but not limited to
 targeted therapies within 6 months of the
 first dose of study intervention.
- Herbal medications with presumed anti-inflammatory properties, or that are known to have an effect on drug metabolism (eg, St. John's Wort) must be discontinued at least 7 days or 5 half-lives (whichever is longer) before the first dose of study intervention.
- Oral and parenteral anti-infectives within 2 weeks or 5 half-lives (whichever is longer) before the first dose of study intervention.
- Herbal and prescription medications for treatment of chronic diseases including but not limited to hematological, renal, endocrine, pulmonary, gastrointestinal, cardiovascular, hepatic, psychiatric, neurological, or allergic disease.
- Any other investigational drug(s) within 4 weeks of the first dose of study intervention or 5 half-lives (whichever is longer), or at any time during the study.

A protocol deviation is to be completed for any participant that takes a prohibited treatment or medication during the study and the sponsor is to be notified.

7. DISCONTINUATION OF STUDY INTERVENTION AND PARTICIPANT DISCONTINUATION/WITHDRAWAL

7.1. Discontinuation of Study Intervention

It may be necessary for a participant to permanently discontinue study intervention. Reasons for permanent discontinuation of study intervention include the following:

 Any participant, who develops Grade 2 or higher AEs for cardiac and blood/bone marrow categories and Grade 3 or higher AEs in all other categories according to criteria defined in CTCAE (version 5), will be discontinued from treatment and followed until resolution of the AE(s);

- If a participant experiences symptoms typical of an allergic reaction (see Section 7.1.6 for temporary discontinuation and rechallenge in Part B), the study drug administration should be discontinued immediately and permanently,
- ECG changes (see Section 7.1.2);
- Unacceptable toxicity as judged by the investigator;
- Pregnancy.

Note that discontinuation of study intervention does not represent withdrawal from the study. If study intervention is permanently discontinued, the participant should remain in the study to be evaluated for 5 half-lives after last dose. See the SoA for data to be collected at the time of discontinuation of study intervention and follow-up for any further evaluations that need to be completed.

In the event of discontinuation of study intervention, it must be documented on the appropriate CRF/in the medical records whether the participant is discontinuing further receipt of study intervention or also from study procedures, posttreatment study follow-up, and/or future collection of additional information.

7.1.1. Liver Injury

A participant who meets the criteria as described in Appendix 6 will be withdrawn from study intervention (if in MD cohort).

7.1.2. ECG Changes

A participant who meets the bulleted criteria based on the average of triplicate ECG readings will be withdrawn from the study intervention.

- QTcF >500 ms.
- Change from baseline: QTcF >60 ms.

If a clinically significant finding is identified (including, but not limited to, changes from baseline in QTcF after enrollment), the investigator or qualified designee will determine if the participant can continue in the study and if any change in participant management is needed. This review of the ECG printed at the time of collection must be documented. Any new clinically relevant finding should be reported as an AE.

7.1.3. Potential Cases of Acute Kidney Injury

Abnormal values in SCr concurrent with presence or absence of increase in BUN that meet the criteria below, in the absence of other causes of kidney injury, are considered potential cases of acute kidney injury and should be considered important medical events. An increase of ≥0.3 mg/dL (or ≥26.5 µmol/L) in SCr level relative to the participant's own baseline measurement should trigger another assessment of SCr as soon as practically feasible, preferably within 48 hours from awareness.

If the second assessment (after the first observations of ≥0.3 mg/dL [or ≥26.5 µmol/L] in SCr relative to the participant's own baseline measurement) is ≥0.4 mg/dL (or ≥35.4 µmol/L), the participant should be discontinued from the study and adequate, immediate, supportive measures taken to correct apparent acute kidney injury.

Participants should return to the investigator site and be evaluated as soon as possible, preferably within 48 hours from awareness of the second assessment confirming abnormal SCr result. This evaluation should include laboratory tests, detailed history, and physical assessment. In addition to repeating SCr, laboratory tests should include serum BUN, serum creatine kinase, and serum electrolytes (including at a minimum potassium, sodium, phosphate/phosphorus, and calcium), in addition to urinary dipstick, urine microscopic examination, and urinary indices. All cases confirmed on repeat testing as meeting the laboratory criteria for acute kidney injury, with no other cause(s) of laboratory abnormalities identified, should be considered potential cases of drug-induced kidney injury irrespective of availability of all the results of the investigations performed to determine etiology of the abnormal SCr. If ≥2 healthy participants in a given treatment arm are noted to have 2 consecutive SCr results of ≥0.3 mg/dL (or ≥26.5 µmol/L), an assessment of whether the finding may be considered an adverse drug reaction should be undertaken.

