7.1.4. Pregnancy

Pregnancy tests are conducted as per SoA and dosing of study intervention will occur only in the presence of a negative pregnancy test. If a participant is confirmed to be pregnant (see Section 8.3.6) during any visit, further dosing with study intervention (if in the MD cohorts) will be discontinued immediately and permanently.

Section 8.4.5.1 Exposure During Pregnancy describes the follow-up activities if a participant meets the EDP criteria.

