7.2. Participant Discontinuation/Withdrawal From the Study

A participant may withdraw from the study at any time at their own request. Reasons for discontinuation from the study include the following:

- Refused further study procedures;
- Lost to follow-up;
- Death;
- Study terminated by sponsor.

At the time of discontinuing from the study, if possible, an early discontinuation visit should be conducted. See the SoA for assessments to be collected at the time of study discontinuation and follow-up and for any further evaluations that need to be completed.

The early discontinuation visit applies only to participants who are enrolled/randomized and then are prematurely withdrawn from the study. Participants should be questioned regarding their reason for withdrawal.

If a participant withdraws from the study, they may request destruction of any remaining samples taken and not tested, and the investigator must document any such requests in the site study records and notify the sponsor accordingly.

If the participant withdraws from the study and also withdraws consent (see Section 7.2.1) for disclosure of future information, no further evaluations will be performed and no additional data will be collected. The sponsor may retain and continue to use any data collected before such withdrawal of consent.

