8.3.4. Clinical Safety Laboratory Assessments

See Appendix 2 for the list of clinical safety laboratory tests to be performed and the SoA for the timing and frequency. All protocol-required laboratory assessments, as defined in Appendix 2, must be conducted in accordance with the laboratory manual and the SoA. Unscheduled clinical laboratory measurements may be obtained at any time during the study to assess any perceived safety issues.

The investigator must review the laboratory report, document this review, and record any clinically significant changes occurring during the study in the AE section of the CRF. Clinically significant abnormal laboratory test findings are those that are not associated with the underlying disease, unless judged by the investigator to be more severe than expected for the participant's condition.

All laboratory tests with values considered clinically significant and abnormal during participation in the study or within 90 days after the last dose of study intervention should be repeated until the values return to normal or baseline or are no longer considered clinically significant by the investigator or study medical monitor.

If such values do not return to normal/baseline within a period of time judged reasonable by the investigator, the etiology should be identified and the sponsor notified.

See Appendix 6 for suggested actions and follow-up assessments in the event of potential DILI.

See Appendix 7 for instructions for laboratory testing to monitor kidney function and reporting laboratory test abnormalities.

Participants may undergo random urine drug testing at the discretion of the investigator. Drug testing results conducted prior to dosing must be in alignment with Section 5.2 Exclusion Criterion 10 for participants to receive study intervention.

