8.4.1. Time Period and Frequency for Collecting AE and SAE Information

The time period for actively eliciting and collecting AEs and SAEs ("active collection period") for each participant begins from the time the participant provides informed consent, which is obtained before undergoing any study -related procedure and/or receiving study intervention), through and including a minimum of approximately 5 half-lives or until their exposures are below LLOQ after the last administration of the study intervention.

Follow-up by the investigator continues throughout the active collection period and until the AE or SAE or its sequelae resolve or stabilize at a level acceptable to the investigator.

When a clinically important AE remains ongoing at the end of the active collection period, follow-up by the investigator continues until the AE or SAE or its sequelae resolve or stabilize at a level acceptable to the investigator and Pfizer concurs with that assessment.

For participants who are screen failures, the active collection period ends when screen failure status is determined.

If the participant withdraws from the study and also withdraws consent for the collection of future information, the active collection period ends when consent is withdrawn.

If a participant permanently discontinues or temporarily discontinues study intervention because of an AE or SAE, the AE or SAE must be recorded on the CRF and the SAE reported using the CT SAE Report Form.

Investigators are not obligated to actively seek information on AEs or SAEs after the participant has concluded study participation. However, if the investigator learns of any SAE, including a death, at any time after a participant has completed the study, and they consider the event to be reasonably related to the study intervention, the investigator must promptly report the SAE to Pfizer using the CT SAE Report Form.

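### The kidney-injury rule (Protocol 7.1.3) takes a participant out of the study, where its parent section and the mandatory actions of its sibling rules stop only the drug

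*Protocol*

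**What the plan says.** Section 7.1.3 sets a two-step rule. A creatinine rise of at least 0.3 mg/dL over the participant's own baseline triggers a repeat test, preferably within 48 hours. If the repeat reaches 0.4 mg/dL (read here as a rise from baseline), "the participant should be discontinued from the study and adequate, immediate, supportive measures taken to correct apparent acute kidney injury". The section then asks for a return visit and a renal work-up.

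The parent section, 7.1, covers discontinuation of study intervention. It notes that stopping the drug is not withdrawal from the study, and adds: "If study intervention is permanently discontinued, the participant should remain in the study to be evaluated for 5 half-lives after last dose".

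The neighbouring rules read as follows:

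- Liver (7.1.1): the participant "will be withdrawn from study intervention (if in MD cohort").
- ECG (7.1.2): a participant meeting a QTcF threshold "will be withdrawn from the study intervention". Separately, the investigator decides whether a participant with a clinically significant ECG finding can continue in the study.
- Pregnancy (7.1.4): "further dosing with study intervention (if in the MD cohorts) will be discontinued immediately and permanently".

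For those who leave the study, Section 7.2 states: "At the time of discontinuing from the study, if possible, an early discontinuation visit should be conducted". It also refers to the Schedule of Activities (SoA) for any further evaluations.

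**The concern.** The protocol treats the study and the study intervention as different things. Section 7.2.1 keeps even participants who ask to stop the drug in follow-up. A site applying 7.1.3 as written would take the participant off the visit schedule, which 7.1 and the mandatory sibling actions do not do.

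Section 7.1.3 itself classes confirmed, otherwise unexplained cases as potential drug-induced kidney injury. In a first-in-human study of an antibody engineered for a longer half-life, later concentration, ADA, laboratory and ECG data from such a participant help in judging causality. Each participant also carries weight: Cohorts 1 and 2 have 2 active participants each (Section 4.1.1), and Section 4.2 allows replacement only for discontinuations other than for safety reasons.

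**Working it through.** No statistical figure is at issue. The check is a comparison of texts, then a count of scheduled visits.

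**Step 1. Required action, rule by rule**

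| Protocol section | Mandatory action | Leaves the study? |
|---|---|---|
| 7.1 (parent) | Stop drug | No; evaluated for 5 half-lives |
| 7.1.1 liver | Stop drug, multiple-dose (MD) cohorts | No |
| 7.1.2 QTcF threshold | Stop drug | No (separate investigator decision for significant findings) |
| 7.1.3 kidney | Discontinue from study | Yes |
| 7.1.4 pregnancy | Stop further dosing, MD cohorts | No |

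Nothing in 7.1.3 exempts kidney cases from 7.1, and no other section puts them back on the scheduled SoA visits.

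**Step 2. What continues regardless**

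- 7.1.3 requires the renal evaluation.
- 8.3.4 has clinically significant abnormal laboratory tests, during participation or within 90 days of the last dose, "repeated until the values return to normal or baseline or are no longer considered clinically significant".
- 8.4.1 and 8.4.3 have the adverse event followed until it resolves or stabilises.
- 8.4.1 sets active adverse event collection for each participant at a minimum of about 5 half-lives, or until exposure is below the quantification limit.

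**Step 3. Scheduled visits forgone under a literal reading**

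Inputs: SoA Table 2 (Part A) and Table 5 (Part B). Assumption: the repeat creatinine falls 2 days after the scheduled laboratory visit and the participant leaves then.

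Part A, Day 15 laboratory visit, leaving at 15 + 2 = Day 17:

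- PK/ADA: Days 32, 46, 61, 91, 181, 211, 241, 271, 301, 331, 361, 451 = 12.
- Safety laboratory: Days 32, 46, 61, 91, 181, 271, 361, 451 = 8.
- ECG: Days 32, 61, 91, 181, 271, 361, 451 = 7.

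Part B, Day 36 laboratory visit, leaving at 36 + 2 = Day 38:

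- PK/ADA: Days 51, 66, 81, 111, 171, 201, 231, 261, 291, 321, 351, 381, 471 = 13.
- Safety laboratory: Days 51, 66, 81, 111, 201, 291, 381, 471 = 8.
- ECG: Days 51, 81, 111, 201, 291, 381, 471 = 7.

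The loss shrinks with time. In Part A, leaving at about Day 34 (after the Day 32 visit) forgoes 12 − 1 = 11 PK/ADA visits, 8 − 1 = 7 with laboratory tests and 7 − 1 = 6 with ECG. Leaving at about Day 273 (after the Day 271 visit) forgoes 4 PK/ADA visits (Days 301, 331, 361, 451), of which 2 (Days 361 and 451) include laboratory tests and ECG.

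Against each count stands the early-discontinuation visit, which in both tables includes safety laboratory tests, PK and ADA sampling.

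**Step 4. Exposure avoided by leaving**

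In Part A it is none, because the single dose has already been given. In Part B, withdrawing study intervention alone prevents a remaining dose just as well.

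**The case against.** The strongest reply is that 'study' in 7.1.3 is a slip for 'study intervention', that the parent section supplies the right reading, and that the verb is 'should'. That is plausible. It is also a reason to correct the phrase, because the protocol uses both terms deliberately elsewhere and a site should not have to guess.

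Several further objections stand and limit the point:

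- A reader might infer that 7.1.3 is the only rule that contemplates leaving the study. It is not: 7.1.2 leaves that decision to the investigator for significant ECG findings. Only 7.1.3 directs it at a fixed threshold.
- A reader might infer from 7.2 that kidney injury is not a permitted reason to leave. That list is introduced as what the reasons include, so it need not be exhaustive. Section 7.2 also allows for further evaluations beyond a single visit.
- A reader might infer that new adverse events stop being collected. Section 8.4.1 does say "Investigators are not obligated to actively seek information on AEs or SAEs after the participant has concluded study participation". But it also sets the minimum of about 5 half-lives for each participant, and the early endings it names are screen failure and withdrawal with withdrawn consent. Continued collection is the better reading.
- A reader might describe nearly all of the follow-up period as uncovered. That would ignore the continuing renal and adverse event follow-up, and it would depend on choosing an early event date.
- The 5-half-life sentence in 7.1 applies when study intervention is permanently discontinued. A single-dose participant has none left to discontinue, so Part A follow-up rests on Section 4.1.1.

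**Conclusion.** The conflict is real and should be corrected, on a modest scale. A literal reading of 7.1.3 would end scheduled safety-laboratory, ECG, PK and ADA follow-up for a participant with possible drug-induced kidney injury, and in Part A would prevent no exposure in return. It would not end follow-up of the creatinine abnormality or of the adverse event.

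The size is per affected participant, since the documents give no event rate. It rests on the current SoA, whose final visit may come earlier in Part A and earlier or later in Part B (Sections 4.1.1 and 4.1.2), and on the assumed 2-day repeat test. The Day 17 and Day 38 cases are illustrations of early events. No hypothesis test or sample-size calculation depends on the phrase.

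**What to change.** In Section 7.1.3, replace the instruction to discontinue the participant from the study with the action used in 7.1.1: the participant "will be withdrawn from study intervention (if in MD cohort"). Then add: *The participant remains in the study and continues SoA follow-up (Sections 4.1.1, 4.1.2 and 7.1), in addition to the renal evaluation below.* Citing 4.1.1 and 4.1.2 matters because the 5-half-life condition in 7.1 does not strictly reach single-dose participants.

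The cost is one phrase and one sentence in a protocol amendment. No visits, samples or CRF fields are added, and a participant may still choose to leave at any time under 7.2.

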7.1.4. Pregnancy

Pregnancy tests are conducted as per SoA and dosing of study intervention will occur only in the presence of a negative pregnancy test. If a participant is confirmed to be pregnant (see Section 8.3.6) during any visit, further dosing with study intervention (if in the MD cohorts) will be discontinued immediately and permanently.

Section 8.4.5.1 Exposure During Pregnancy describes the follow-up activities if a participant meets the EDP criteria.

7.1.5. COVID-19

If a participant has COVID-19 during the study, this should be reported as an AE or SAE (as appropriate) and appropriate medical intervention provided. Temporary discontinuation of the study intervention (for the Part B-MD) may be medically appropriate until the participant has recovered from COVID-19.

It is recommended that the investigator discuss temporary or permanent discontinuation of study intervention with the study medical monitor.

7.1.6. Temporary Discontinuation

If a participant experiences symptoms typical of infusion reactions (eg, lightheadedness, nausea, chills, fever) or mild immunogenicity reactions, the study intervention infusion should be stopped. At the discretion of the investigator, the infusion can be restarted at a

slower rate if symptoms are resolved within 1 hour after the stop of infusion. If symptoms return, then the study intervention administration should be discontinued immediately and permanently.

In the event that there is an infusion interruption, the entire duration of drug infusion, from the initial start of infusion to the completion of infusion, should not exceed 3 hours. The start and stop time of the infusion and the infusion rate and amount of volume infused in the event of an interruption will be recorded. Participants will receive appropriate treatment at the discretion of the investigator.

For MD cohorts, if participants miss the scheduled second dosing visit window (approximately a week), this will be considered a temporary study drug interruption and a protocol deviation. Participants will be contacted and further dosing decisions will be based on discussions between investigators and sponsor.

Participants in multiple dose cohorts who may have had mild/moderate injection site reaction(s), may receive the second scheduled dose of study intervention at the discretion of the investigator.

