2.3.1. Risk Assessment

Potential Risk of Clinical Significance	Summary of Data/Rationale for Risk	Mitigation Strategy
	Study Intervention(s) PF-07261271 and Placebo	
Potential for anaphylaxis, infusion reactions, and injection site reactions.	As a protein therapeutic, there is a theoretical potential for immunotoxicity. The potential for PF-07261271 to induce significant antibody responses and for such antibody responses, should they occur, to cause clinically significant sequelae has been assessed based on the physical characteristics of PF-07261271, the planned clinical indication, and the design characteristics of the FIH study C4631001. The overall risk of immunogenicity is projected to be moderate.	Participants will be observed closely for signs and symptoms of infusion reactions and anaphylaxis using standard clinical monitoring, specifically for targeted AEs. Infusion of the study intervention will be interrupted and the rate reduced should mild infusion reactions be observed. If the reactions persist, the infusion will be stopped and the participant observed until stable. In the event of more severe infusion reactions or anaphylaxis, the infusion will be stopped and no re-challenge will be performed. All anaphylactic reactions will be assessed by Sampson's criteria. For SC administration of study treatment, injection site reactions will be monitored, and injection sites rotated.
Risk of infection	All therapeutics designed to reduce inflammation have the potential risk of immune suppression that could result in serious infection.	Participants will be screened and excluded if they have active or latent infections. They will be monitored for evidence of infection with laboratory testing and AE surveillance.
	Study Procedures	
Extravasation of PF-07261271 and hematomas may occur after IV dosing.	In some cohorts, PF-07261271 will be administered intravenously.	Skilled nurses or phlebotomists will insert indwelling catheters for infusion and ensure that they are correctly placed in a vein. The infusion site will be monitored for development of hematomas and extravasation. In the event of an issue, the infusion will be interrupted and the catheters will be replaced.
	Other	
The COVID-19 pandemic may pose risks to study participation.	Participants may have increased risk of SARS-CoV-2 infection by undergoing a study procedure at a study facility.	Inclusion of COVID-19 specific screening procedures and assessments according to the Schedule of Activities.

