6.1.1. Administration

PF-07261271 and placebo will be administered IV or SC.

Part A: Participants will receive study intervention (start time of infusion) at approximately 0800 hours (±3 hours). For planned IV dosing (Cohorts 1-4, 7, and 8), study intervention will be administered as an intravenous infusion over the description volumes and rates will be provided in the IP manual, which may supersede the descriptions in the protocol. In the case of mild infusion reactions, at the discretion of the investigator, the infusion may be interrupted and restarted at a slower infusion rate not to exceed a total administration duration of the infusion. The start and stop time of the infusion will be recorded in source document and CRF. Time 0 is the time when the study intervention infusion begins. The exact injection volume (for IV injections), infusion rate, and the volume infused will be recorded.

Part B: For Cohort 5, study intervention is planned to be administered SC at approximately 0800 hours (±3 hours). Cohort 6 is optional and may be administered either SC or IV. SC injections can be administered in the abdomen, thigh, back of arms or as outlined in the IP manual. The preferred body location for the SC injection is the abdomen. If abdominal injections are not possible, arm or thigh locations may also be used. The total dose volume may be divided into an appropriate number of syringes for administration according to local site practice. Where multiple SC injections may be required to make up the total SC dose, it is preferable to administer each of the SC injections in the same body location but spaced slightly apart. Signs of infection/inflammation in the injection area after discharge should be reported immediately to the investigator. Further details on administration including injection volumes and sites will be provided in the IP manual.

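### Protocol Sections 2.3.1, 6.1.1, 7.1 and 7.1.6 are inconsistent on when an infusion may be restarted after a reaction

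*Protocol*

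**What the plan says.** Four places in the protocol deal with a reaction during an infusion.

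- **Section 2.3.1 (risk table).** For mild reactions: "Infusion of the study intervention will be interrupted and the rate reduced should mild infusion reactions be observed". For persisting ones: "If the reactions persist, the infusion will be stopped and the participant observed until stable". For the rest: "In the event of more severe infusion reactions or anaphylaxis, the infusion will be stopped and no re-challenge will be performed".
- **Section 6.1.1 (Part A paragraph).** "In the case of mild infusion reactions, at the discretion of the investigator, the infusion may be interrupted" and restarted more slowly. There is a cap on total duration, but its value is blacked out.
- **Section 7.1.** "If a participant experiences symptoms typical of an allergic reaction (see Section 7.1.6 for temporary discontinuation and rechallenge in Part B"), administration is to end at once and for good. A separate bullet discontinues anyone with a CTCAE Grade 3 or higher event, or Grade 2 or higher in the cardiac and blood/bone marrow categories.
- **Section 7.1.6.** "If a participant experiences symptoms typical of infusion reactions (eg, lightheadedness, nausea, chills, fever) or mild immunogenicity reactions", the infusion is stopped. The investigator may then restart it at a "slower rate if symptoms are resolved within 1 hour after the stop of infusion". If symptoms come back, the stop is permanent. An interrupted infusion may last at most 3 hours in total. The only text here on reactions in the multiple-dose cohorts concerns injection site reactions and the second dose.

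**The concern.** Infusion reactions and anaphylaxis belong to the first potential risk listed in Section 2.3.1, for a molecule not previously given to humans and with a projected moderate risk of immunogenicity. The decision to restart is made at the bedside, and staff will follow whichever section they have in front of them. If one section permits a restart that another rules out, the same reaction can be handled in two ways without either being a clear deviation.

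The choice also affects the data. A restarted participant may receive the whole dose, more slowly; a permanently stopped one receives part of it and is counted as discontinued. Escalation depends on group mean exposure (Sections 4.1.1 and 6.6.1), and Section 6.6 requires safety and PK data from all participants in Cohorts 1 and 2. SAP Section 4.2 allows participants with events that may affect their PK profile to be left out of the PK analysis. Inconsistent handling can therefore influence which exposures are averaged, in groups of 2 to 6 active participants.

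**Working it through.** The plan gives no figure to reproduce, so the check applies each section's rule to the same reaction profile.

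| Profile | 2.3.1 | 6.1.1 | 7.1 | 7.1.6 | Result |
|---|---|---|---|---|---|
| (a) Mild, not allergic, resolved within 1 hour | Interrupt, reduce rate | Restart permitted | Not triggered | Restart permitted | Agree |
| (b) More than mild, below the 7.1 grades, resolved within 1 hour | Re-challenge barred if this counts as more severe | Does not extend to it | Graded rule not triggered | Restart permitted | Conflict |
| (c) Grade 3 or higher | Re-challenge barred if this counts as more severe | Does not extend to it | Discontinue | Not excluded, no reference to the graded rule | Settled by 7.1; link missing |
| (d) Mild allergic or immunogenicity-type symptoms, Part A | Not addressed separately | Restart permitted if called a mild infusion reaction | Permanent stop; rechallenge mentioned only for Part B | Restart permitted in any part | Conflict |
| (e) Mild, resolved after more than 1 hour | Stop if it persists; no time given | No time condition stated | Not triggered | Restart condition not met | Inconsistent |

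**Severity, row (b).** In 7.1.6 the word mild is attached to immunogenicity reactions and not to infusion reactions. In 2.3.1 and 6.1.1 it is attached to infusion reactions. What 2.3.1 means by more severe is not defined. Appendix 3 (Section 10.3.3) has a mild/moderate/severe intensity scale and 7.1 uses CTCAE grades, but 2.3.1, 6.1.1 and 7.1.6 refer to neither.

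**Symptom category, row (d).** The documents do not separate allergic symptoms from mild immunogenicity reactions. Section 4.2 counts infusion reactions and anaphylaxis among the manifestations of immunogenicity. Section 8.3.7 lists erythema and pruritus as signs of infusion or injection site reactions, and Appendix 9 lists pruritus and flushing as skin involvement. Mild itching during an infusion could be placed under either rule.

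**The pointer to Part B.** Cohorts 1-4 are IV and in Part A. Cohort 5 in Part B is planned as SC. Only optional Cohort 6 could bring an infusion into Part B. The infusions that are certain to be planned therefore lie outside the part that the pointer names.

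**Numbers who could be exposed to the conflict (Section 4.1.1).**

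- Non-optional IV participants, Cohorts 1-4: 4 + 4 + 6 + 8 = 22; active 2 + 2 + 4 + 6 = 14.
- Adding optional Cohort 7: 22 + 8 = 30; active 14 + 6 = 20.
- Adding optional Cohorts 6 and 8, if both are IV: 30 + 8 + 5 = 43; active 20 + 6 + 4 = 30.
- Weight of one active participant in the active group: 1/2 in Cohorts 1 and 2, 1/4 in Cohort 3, 1/6 in Cohort 4.

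These are upper bounds on who could be affected. The documents give no expected rate of infusion reactions, and none is assumed here.

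**The case against.** The best defence has four parts.

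1. **Severe reactions are already covered.** The graded rule in 7.1, the parent section of 7.1.6, discontinues at Grade 3 or higher (Grade 2 or higher for cardiac and blood/bone marrow events). This stands. A reader might infer from 7.1.6 alone that any reaction may be restarted whatever its severity; the documents do not support that. If more severe in 2.3.1 means Grade 3 or higher, row (b) shrinks to the narrower mild-only wording of 6.1.1. Rows (d) and (e) are untouched.
2. **Restart is discretionary.** An investigator who always follows the strictest section breaches none of them, and 7.1.6 also requires a stop, a permanent stop on recurrence and a 3-hour limit. This also stands: opposite handling of the same reaction is permitted, not certain, and the protocol does not commit to more than one site. But a permission set beside a prohibition still leaves staff without one rule.
3. **The pointer in 7.1 links rule and exception.** Only in part. It names Part B alone, while the text it leads to covers infusions in any part.
4. **Section 2.3.1 is a summary table, and 6.1.1 defers to a manual.** The table nonetheless states what will be done. The deference in 6.1.1, as far as it is legible, concerns infusion volumes and rates, and the manual is not among the documents.

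The effect on the analysis is also modest: no hypothesis is tested, one dose suffices for the safety set, and 7.1.6 requires the rate and volume of an interrupted infusion to be recorded.

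**Conclusion.** The inconsistency is real and lies in current text. It has four components: the severity limit (2.3.1 and 6.1.1 against 7.1.6), allergic against mild immunogenicity reactions (7.1 against 7.1.6), the Part B pointer in 7.1, and the 1-hour condition that 6.1.1 does not state. The severity component is mainly open for more-than-mild reactions below the grades in 7.1, and its width depends on what more severe is meant to cover. The sections agree on a mild, non-allergic reaction that resolves within 1 hour.

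Three further inferences are not supported. Not every IV participant is affected, only those who have a reaction in the disputed range. Section 7.1.6 does not say whether symptoms controlled by treatment count as resolved, but no other section says otherwise, so that is missing detail and not a contradiction. The duration cap in 6.1.1 cannot be compared with the 3 hours in 7.1.6 because its value is blacked out.

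The number affected is likely to be small, but the point deserves correction because it governs an acute safety decision in a first-in-human study, and because one active participant is half of the active group in Cohorts 1 and 2.

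**What to change.** Reconcile Sections 2.3.1, 6.1.1, 7.1 and 7.1.6 into a single rule, stated once and cross-referred to from the other places. The rule should:

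- use the same severity terms throughout, tied to a scale the protocol already contains;
- say which infusion, allergic and immunogenicity symptoms fall under restart and which under permanent discontinuation;
- refer explicitly to the graded adverse event rule in 7.1;
- state whether the 1-hour condition applies wherever restart is mentioned;
- correct or remove the pointer to rechallenge in Part B.

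Which rule applies is for the sponsor's clinicians to decide; this point proposes none. The investigational product manual should be checked for consistency with the result.

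The cost is a wording amendment with the ethics review that Section 10.1.1 requires. No visit, assessment, sample size or analysis changes.
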